6.5.6 Pregnancy and assessments of fertility

A serum or plasma pregnancy test will be performed at the screening visit and urine pregnancy test will be performed at study completion. All female patients in this study must undergo obligatory pregnancy testing as per schedule of assessment ([Table 6-1](#)).

6.5.7 Appropriateness of safety measurements

The safety assessments selected are standard for this indication/patient population.

6.5.8 Definition of Treatment Failure

Early treatment failure (ETF)

ETF is defined within this protocol as:

1. Clinical decline or lack of improvement (per Investigator) at 24 hours after first dose of treatment.
2. Development of any clinical complications (described in the WHO definition of complicated/severe malaria (WHO Guidelines 2010)) in the presence of parasitaemia within 72 hours of the first dose of treatment
3. Parasitaemia > 75 000/ μ L at or after 12 hours post-dose
4. Parasitaemia \geq baseline with or without fever at 36 hours after first dose of treatment
5. Any parasitaemia based on microscopy with fever, 48 hours post-dose
6. Parasitaemia > 100/ μ L based on microscopy with or without fever, 72 hours post-dose

Late Clinical Failure (LCF)

Development of danger signs or severe malaria on any day between Study Day 5 and Day 29 in the presence of parasitaemia without previously meeting any of the criteria of ETF

Presence of parasitaemia and axillary temperature $\geq 37.5^{\circ}\text{C}$ on any day between Study Day 5 and Day 29 without previously meeting any of the criteria of ETF

Late Parasitological Failure (LPF)

Presence of parasitaemia on any day between Study Day 5 and Day 29 and axillary temperature $< 37.5^{\circ}\text{C}$ without previously meeting any of the criteria of ETF or LCF

Adequate Clinical and Parasitological Response (ACPR):

Absence of parasitaemia on Study Day 29 irrespective of axillary temperature, without previously meeting any of the criteria of ETF or Late Treatment Failure or LPF.

Note: The first day of treatment with study medication is defined as Study Day 1 while the day prior to the first day of treatment is defined as Day -1. Compared to [WHO \(2016\)](#) which defined Day 0 as the first day of treatment with study medication, days after treatment referred to in this protocol are 1 day greater. For example, Study Day 29 in this protocol corresponds to Day 28 by [WHO \(2016\)](#).

Signs/symptoms indicative of severe/complicated malaria

Danger signs:

1. not able to drink
2. vomiting $>$ twice within preceding 24 hours
3. one convulsion within preceding 24 hours
4. unconscious state
5. unable to sit or stand

Signs of severe malaria:

Severe falciparum malaria is defined as one or more of the following, occurring in the absence of an identified alternative cause and in the presence of *P. falciparum* asexual parasitaemia:

- Impaired consciousness (Glasgow coma score < 11 in adults)
- Prostration (generalized weakness i.e., unable to sit, stand or walk without assistance)
- Multiple convulsions (more than two episodes within 24 hours)
- Acidosis (a base deficit of > 8 mEq/L or if not available a plasma bicarbonate level of < 15 mmol/L or venous plasma lactate ≥ 5 mmol/L. severe acidosis manifests clinically as respiratory distress i.e., rapid, deep, laboured breathing)
- Hypoglycemia (blood or plasma glucose < 2.2 mmol/L; < 40 mg/dL)
- Severe malarial anemia (haemoglobin concentration < 7 g/dL or haematocrit of $< 20\%$ in adults with a parasite count $> 10\,000/\mu\text{L}$)
- Renal impairment (plasma or serum creatinine > 265 $\mu\text{mol/L}$ (3 mg/dL) or blood urea > 20 mmol/L)
- Jaundice (plasma or serum bilirubin > 50 $\mu\text{mol/L}$ (3 mg/dL) with a parasite count $> 100\,000/\mu\text{L}$)
- Pulmonary edema (radiologically confirmed or oxygen saturation $< 92\%$ on room air with a respiration rate $> 30/\text{min}$, often with chest indrawing and crepitations on auscultation)

- Significant bleeding (including recurrent or prolonged bleeding from the nose, gums or venipuncture sites, haematemesis or melaena)
- Shock (compensated shock i.e., capillary refill \geq 3s or temperature gradient on leg but no hypotension; decompensated shock i.e., systolic blood pressure $<$ 80 mm Hg in adults with evidence of impaired perfusion)
- Hyperparasitaemia (*P. falciparum* parasitaemia $>$ 10%)

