##### Early treatment failure (ETF)

Patients will be classified as ETF upon meeting any of the following criteria:

- Clinical decline or lack of improvement (per Investigator) at 24 hours after first dose of treatment.

- Development of any clinical complications (described in the WHO definition of complicated/severe malaria (WHO Guidelines 2010) in the presence of parasitaemia (based on microscopy) within 72 hours of the first dose of treatment
- Parasitaemia  $> 75\,000/\mu\text{L}$  based on microscopy at or after 12 hours post first dose
- Parasitaemia  $\geq$  baseline based on microscopy with or without fever at 36 hours after the first dose of treatment
- Any parasitaemia based on microscopy with fever, 48 hours post first dose
- Parasitaemia  $> 100/\mu\text{L}$  based on microscopy with or without fever, 72 hours post first dose

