### **Uncorrected ACPR at Day X where X=15 and 29**

- A patient is considered as non-responder at Day X if the patient experiences an ETF, LCF or LPF from Day 5 to Day X.
- A patient is also considered as non-responder if the parasitaemia is not cleared by Day X unless the patient discontinues the study prior to Day X without ETF, LCF, or LPF in which case the response is considered as missing.

- A patient is considered as responder (Uncorrected ACPR) at Day X if the patient is not classified as a non-responder at Day X and the patient has a malaria blood film showing absence of parasitaemia at Day X or later if Day X is missing.
- The response for a patient is considered as missing/undertermined if the patient is not classified as a non-responder and the malaria blood film result at Day X is missing and not followed by a subsequent negative result.

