### **Handling of missing values/censoring/discontinuations**

Patients whose outcome status cannot be determined due to incomplete/missing data will be excluded from analysis. Especially, the denominator is the number of patients who experience treatment failure or have malaria blood film result at Day 29 for LCF and LPF. Patients with ETF will be excluded from the analysis of LCF and patients with ETF or LCF will be excluded from the analysis of LPF.

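### The high-density ETF criterion has no end time, so a first late recurrence above 75 000/µL is tabulated as early failure and leaves the late-failure analyses

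*Protocol*

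**What the plan says.** Protocol 6.5.8 lists six ETF criteria, and 5.5.6 repeats them as grounds for stopping treatment and giving rescue. Five have a fixed time point or a closing time. Criterion 3, parasitaemia above 75 000/µL, applies "at or after 12 hours post-dose". SAP 2.1.1.1 words it as "based on microscopy at or after 12 hours post first dose". That settles which dose starts the clock but sets no end.

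Criterion 2 (clinical complications) applies "in the presence of parasitaemia within 72 hours of the first dose of treatment". Criterion 6 (above 100/µL) is set at 72 hours.

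Late failure has its own window. The first LCF criterion is "Development of danger signs or severe malaria on any day between Study Day 5 and Day 29 in the presence of parasitaemia", provided no ETF criterion was met previously. LPF uses the same days and the same proviso.

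SAP 2.7.2.2 sets the order of precedence in the tables: "Patients with ETF will be excluded from the analysis of LCF", and patients with ETF or LCF are left out of the LPF analysis. All three proportions use uncorrected parasite counts (Protocol 9.5.1.2, SAP 2.7.2.2).

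**The concern.** ETF and late failure answer different questions. ETF describes failure to control the infection present at entry. LCF and LPF describe persistence or return of parasites from Study Day 5. An open-ended criterion 3 lets an event of the second kind be counted as the first.

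The proportions with ETF, LCF and LPF are three listed secondary efficacy variables, each reported by arm with an exact interval. KAE609 arms have 10 or 20 patients, so one misplaced patient is visible. The dose would look worse at initial control and better on late failure than it was. Separately, the ETF and LCF windows for clinical complications do not quite meet on Study Day 4.

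**Working it through.** The plan states no figure on this point, so there is none to reproduce. The check sets the windows side by side and then moves one patient.

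**1. Windows (Protocol 6.5.8, SAP 2.1.1.1)**

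| Criterion | Window |
|---|---|
| ETF 1, lack of improvement | 24 h |
| ETF 2, complications with parasitaemia | up to 72 h |
| ETF 3, above 75 000/µL | 12 h onward, no end |
| ETF 4, at or above baseline | 36 h |
| ETF 5, any parasitaemia with fever | 48 h |
| ETF 6, above 100/µL | 72 h |
| LCF, LPF | Study Day 5 to Day 29, no ETF previously |

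No other section limits ETF in time.

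**2. One patient traced.** Suppose (illustration) clearance by Study Day 4 and a first positive film on Study Day 22 at 80 000/µL with fever.
- The film is about 21 × 24 = 504 h after the first dose. 504 ≥ 12 and 80 000 > 75 000, so criterion 3 is met.
- Day 22 lies within Days 5 to 29, there is fever, and no ETF criterion was met before this film, so LCF is met too. Without fever it would be LPF.
- SAP 2.7.2.2 counts the patient in ETF and drops them from the LCF and LPF analyses.

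**3. Size** (exact Clopper-Pearson 95% intervals)

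| Proportion | As written | ETF closed at end of Day 4 |
|---|---|---|
| ETF, n = 10 | 1/10 = 10% (0.3 to 44.5) | 0/10 = 0% (0 to 30.8) |
| ETF, n = 20 | 1/20 = 5% (0.1 to 24.9) | 0/20 = 0% (0 to 16.8) |
| LCF, n = 20 | 1/19 = 5.3% (0.1 to 26.0) | 2/20 = 10% (1.2 to 31.7) |

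The LCF row assumes two late clinical failures, one above 75 000/µL, no other ETF, and a failure or a Day 29 film for everyone. If the recurrence is afebrile, the LPF numerator and denominator each fall by one, and so does the LCF denominator.

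**4. The Day 4 gap.** With the first dose at clock hour h on Day 1, 72 h falls at hour h on Day 4. The time left before Study Day 5 is 24 − h: 16 h for a dose at 08:00, 14 h at 10:00, 10 h at 14:00. Dosing hours are assumed; the documents give none. Most counts in that interval are covered:
- A count above 75 000/µL meets criterion 3.
- SAP Table 5-6 assigns parasite counts from after 66 h to the end of Day 4 to the 72 h time point, and Table 5-7 picks the value closest to target. A selected count above 100/µL therefore meets criterion 6.

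That window covers counts and temperature. It does not extend criterion 2. Complications with parasitaemia that first arise after 72 h on Day 4, without a count meeting criterion 3 or 6, meet no ETF criterion and precede the LCF window. Positives at or below 100/µL, and later Day 4 films that are not selected and are at or below 75 000/µL, also go unclassified that day. Anything persisting into Day 5 is then picked up as LCF or LPF.

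**5. What does not move.** The primary endpoint uses ALT and AST only. In uncorrected ACPR, ETF, LCF and LPF all count as non-response. PCR-corrected ACPR from Day 8 follows the genotype, provided the Day 5 to Day 7 limit in that SAP rule applies to ETF as well as to LCF and LPF; the sentence is ambiguous on this.

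**The case against.** The strongest reply is that little is lost. These are descriptive secondary variables in a hepatic safety study, with no planned comparison with Coartem. Relabelling needs a first positive film already above 75 000/µL, although entry is capped at 50 000/µL and films are windowed at Days 5, 8, 11, 15, 22 and 29. This stands as a limit on importance. It does not supply the missing end time.

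Four stronger readings are tempting, and the documents do not support them.
- *The rest of Day 4 belongs to no category.* Open-ended criterion 3 and the SAP 72 h window cover most Day 4 counts. Only the narrow gap in step 4 remains.
- *The late recurrence disappears from view as a late event.* After clearance before Day 15 it still enters the Kaplan-Meier analysis of recrudescence or reinfection with its own date (SAP 2.7.2.4, 2.7.2.5), and listings of ETF, LCF and LPF are planned.
- *Counting a PCR-confirmed new infection is a fault of criterion 3.* All three failure types use uncorrected counts by design, so LCF and LPF include new infections too.
- *The SAP intends late ETF*, because uncorrected ACPR refers to non-response "if the patient experiences an ETF, LCF or LPF from Day 5 to Day X". If the day range governed ETF, an ETF on Days 1 to 4 would not itself make a patient a non-responder under that rule. The phrase is ambiguous and proves neither reading.

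**Conclusion.** The overlap is real on the text of both documents. As written, a first recurrence above 75 000/µL from Study Day 5 is tabulated as ETF and taken out of the LCF and LPF analyses. Each such patient adds 5 points to ETF in an arm of 20 and 10 points in an arm of 10, and lowers the matching late-failure count. The Day 4 gap is real but narrow.

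The frequency cannot be derived from the documents. Protocol 3.6 gives a recrudescence figure of 36% (4 patients) from an earlier study, but nothing gives the share of recurrences above 75 000/µL. A probability per arm would rest on an unsourced input, so none is claimed. The conclusion assumes the definitions are programmed literally. It concerns three secondary descriptive variables and is worth correcting because the correction is small.

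**What to change.** In SAP 2.1.1.1 and 2.7.2.2, for the tabulated endpoint only:
- Count an ETF criterion as ETF only if it is met by the end of Study Day 4, which matches the end of the 72 h window in Table 5-6.
- Classify complications with parasitaemia arising after 72 h on Study Day 4 as ETF.
- Classify any first failure from Study Day 5 as LCF or LPF, whatever its density.

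Record the departure from the protocol definition in SAP section 4, which at present lists no changes. The SAP history already shows an update after database lock, so the entry should be dated accordingly. The cost is a few sentences and one condition in the derivation program, with no new data.

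Protocol 5.5.6 and 6.5.8 use the same criteria to trigger rescue. The sponsor should reconcile their time limits with the late-failure window. No clinical rule is proposed here.

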6.6.1 Pharmacokinetics

Details on sample collection, numbering, processing and shipment can be found in the Laboratory Manual.

7 Safety monitoring

7.1 Adverse events

An adverse event (AE) is any untoward medical occurrence (e.g., any unfavorable and unintended sign (including abnormal laboratory findings), symptom or disease) in a subject or clinical investigation subject *after providing written informed consent* for participation in the study until the end of study visit. Therefore, an AE may or may not be temporally or causally associated with the use of a medicinal (investigational) product.

In addition, all reports of intentional misuse and abuse of the product are also considered an adverse event irrespective if a clinical event has occurred.

The occurrence of adverse events must be sought by non-directive questioning of the patient at each visit during the study. Adverse events also may be detected when they are volunteered by the patient during or between visits or through physical examination findings, laboratory test findings, or other assessments.

Abnormal laboratory values or test results constitute adverse events only if they fulfill at least one of the following criteria:

- they induce clinical signs or symptoms,
- they are considered clinically significant,
- they require therapy.

Clinically significant abnormal laboratory values or test results must be identified through a review of values outside of normal ranges/clinically notable ranges, significant changes from baseline or the previous visit, or values which are considered to be non-typical in patient with underlying disease. Investigators have the responsibility for managing the safety of individual patient and identifying adverse events. Alert ranges for laboratory and other test abnormalities are included in [Appendix 1](#).

Study drug/treatment includes investigational drug KAE609 (10 mg, 25 mg, 50 mg, 75 mg, 150 mg, 225 mg, or 110 mg) as well as Coartem.

Adverse events must be recorded in the Adverse Events CRF under the signs, symptoms or diagnosis associated with them, accompanied by the following information:

- the Common Toxicity Criteria (CTC) AE grade

If Common Toxicity Criteria for Adverse Events (CTCAE) grading does not exist for an adverse event, use

1= mild

2= moderate

3= severe

4= life-threatening (see [Section 7.2](#) for definition of SAE)

CTCAE Grade 5 (death) is not used, but is collected as a seriousness criteria and also collected in other CRFs (Study Completion, Death/Survival).

There may be cases where a CTCAE with a grade of 4 (life-threatening) may not necessarily be an SAE (e.g., certain laboratory abnormalities in the absence of meeting other seriousness criteria).

- its relationship to the study treatment and the reference product Coartem (Yes/No)
- its duration (start and end dates) or if the event is ongoing an outcome of not recovered/not resolved must be reported.
- whether it constitutes a SAE (see [Section 7.2](#) for definition of SAE) and which seriousness criteria have been met.
- action taken regarding (investigational) treatment

All adverse events must be treated appropriately. Treatment may include one or more of the following:

- no action taken (e.g., further observation only)
- study treatment withdrawn
- concomitant medication or non-drug therapy given
- patient hospitalized/patient's hospitalization prolonged (see [Section 7.2](#) for definition of SAE)
- its outcome (not recovered/not resolved; recovered/resolved; recovering/resolving; recovered/resolved with sequelae; fatal; or unknown)

The action taken to treat the adverse event should be recorded on the Adverse Event CRF.

Once an adverse event is detected, it must be followed until its resolution or until it is judged to be permanent, and assessment must be made at each visit (or more frequently, if necessary) of any changes in severity, the suspected relationship to the study drug, the interventions required to treat it, and the outcome.

Information about common side effects already known about the investigational drug can be found in the IB. This information will be included in the patient informed consent and should

be discussed with the patient during the study as needed. Any new information regarding the safety profile of the medicinal product that is identified between IB updates will be communicated as appropriate. New information might require an update to the informed consent and has then to be discussed with the patient.

The investigator must also instruct each patient to report any new adverse event (beyond the protocol observation period) that the patient, or the patient's personal physician, believes might reasonably be related to study treatment. This information must be recorded in the investigator's source documents; however, if the AE meets the criteria of an SAE, it must be reported to Novartis.

7.2 Serious adverse events

7.2.1 Definition of SAE

An SAE is defined as any adverse event (appearance of (or worsening of any pre-existing)) undesirable sign(s), symptom(s) or medical condition(s) which meets any one of the following criteria:

- is fatal or life-threatening
- results in persistent or significant disability/incapacity
- constitutes a congenital anomaly/birth defect
- requires inpatient hospitalization or prolongation of existing hospitalization, unless hospitalization is for:
 - routine treatment or monitoring of the studied indication, not associated with any deterioration in condition
 - elective or pre-planned treatment for a pre-existing condition that is unrelated to the indication under study and has not worsened since signing the informed consent
 - treatment on an emergency outpatient basis for an event not fulfilling any of the definitions of a SAE given above and not resulting in hospital admission
 - social reasons and respite care in the absence of any deterioration in the patient's general condition
- is medically significant, e.g., defined as an event that jeopardizes the patient or may require medical or surgical intervention.

All malignant neoplasms will be assessed as serious under "medically significant" if other seriousness criteria are not met.

Life-threatening in the context of a SAE refers to a reaction in which the patient was at risk of death at the time of the reaction; it does not refer to a reaction that hypothetically might have caused death if it were more severe.

Medical and scientific judgment should be exercised in deciding whether other situations should be considered serious reactions, such as important medical events that might not be immediately life threatening or result in death or hospitalization but might jeopardize the patient or might require intervention to prevent one of the other outcomes listed above. Examples of such events are intensive treatment in an emergency room or at home for allergic bronchospasm, blood

dyscrasias or convulsions that do not result in hospitalization or development of dependency or abuse.

Any suspected transmission of an infectious agent via a medicinal product is also considered a serious adverse reaction.

7.2.2 SAE reporting

To ensure patient safety, every SAE, regardless of causality, occurring after the patient has provided informed consent and following the last administration of study treatment must be reported to Novartis safety within 24 hours of learning of its occurrence. Any SAEs experienced after the 30 day period after the last study visit should only be reported to Novartis safety if the investigator suspects a causal relationship to study treatment.

All follow-up information for the SAE including information on complications, progression of the initial SAE and recurrent episodes must be reported as follow-up to the original episode within 24 hours of the investigator receiving the follow-up information. An SAE occurring at a different time interval or otherwise considered completely unrelated to a previously reported one must be reported separately as a new event.

Information about all SAEs (either initial or follow up information) is collected and recorded in English in the electronic Serious Adverse Event (eSAE) Form within the Oracle Clinical/Remote Data Capture (OC/RDC) system (wherever available and/or feasible) or on the paper SAE Report Form that should be used as back-up, especially in case where there is no feasibility of the use of eSAE Form. The investigator must assess the relationship of each SAE to the study treatment (KAE609 or Coartem).

SAEs (initial and follow-up) that are recorded electronically in the OC/RDC system should be entered, saved and e-signed within 24 hours of awareness of the SAE or changes to an existing SAE. These data will automatically be submitted to Novartis Chief Medical Office and Patient Safety (CMO&PS) immediately after investigator signature or 24 hours after entry, whichever occurs first.

Follow-up information is submitted as instructed in the investigator folder. Each re-occurrence, complication, or progression of the original event must be reported as a follow-up to that event regardless of when it occurs. The follow-up information should describe whether the event has resolved or continues, if and how it was treated and whether the patient continued or withdrew from study participation.

If the SAE is not previously documented in the IB for KAE609 or Package Insert for Coartem (new occurrence) and is thought to be related to the study treatment a CMO & PS Department associate may urgently require further information from the investigator for health authority reporting. Suspected Unexpected Serious Adverse Reactions (SUSARs) will be collected and reported to the competent authorities and relevant ethics committees in accordance with European Union (EU) Guidance 2011/C 172/01 or as per national regulatory requirements in participating countries.

